8.1.3 Geometric Mean Fold Rise

For the ALS titer, the fold rise will be calculated after the first vaccination (post vaccination 1 antibody titer/baseline antibody titer), after the second vaccination (post vaccination 2 antibody titer/baseline antibody titer), and after the second vaccination compared to first vaccination (post vaccination 2 antibody titer/post vaccination 1 antibody titer). The number of observations, GMFR and 95% confidence intervals for the GMFR will be reported. The GMFR will be calculated as the antilog of the mean of the logarithms of the calculated fold rise. The 95% CIs for the GMFR will be based on the t-distribution to provide population estimates and will be presented as the antilog. Pairwise comparisons of the logs of the fold-rise will be performed using a t-test. If the values deviate from the log normal distribution, a non-parametric method (i.e., Wilcoxon) may be used for the analysis of the fold rise.

Tables 14.2.6.1 (a)(b)(c)(d) - 14.2.6.2 (a)(b)(c)(d) will summarize the GMFRs and 95% CIs for the GMFRs for each antigen and treatment group for the FA population and the PP population, respectively. In addition, the p-value from a t-test for each treatment group comparison will be presented for each time period and antigen as shown in Tables 14.2.7.1 (a)(b)(c)(d) - 14.2.7.2(a)(b)(c)(d) for the FA population and the PP population, respectively.

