8.3 Plasma ELISA Antibodies

For ELISA IgA, tables will be presented by antigen in the order of priority as specimen volumes allow. The order of the antigens will be: LTB, 078 LPS, CFA/I, CS3, CS6, and CS5. For ELISA IgG, only LTB and 078S LPS will be analyzed. Immune responses as measured by ELISA IgA and IgG after each vaccination (Day 7 and Day 19 samples) will be evaluated by the following:

- the percentage of participants achieving an IgA antibody response after the first vaccination (i.e., antibody response is calculated using baseline and Day 7 sample) for LTB, 078 LPS, CFA/I, CS3, CS6, and CS5;
- the percentage of participants achieving an IgA antibody response after the second vaccination (i.e., antibody response is calculated using baseline and Day 19 sample) for LTB, 078 LPS, CFA/I, CS3, CS6, and CS5;
- the percentage of participants achieving an IgA antibody response after either vaccination (i.e., antibody response observed after either vaccination) for LTB, 078 LPS, CFA/I, CS3, CS6, and CS5;
- the IgA geometric mean titer (GMT) of LTB, 078 LPS, CFA/I, CS3, CS6, and CS5 at screening and after each vaccination;
- the IgA geometric mean fold rise(GMFR) of LTB, 078 LPS, CFA/I, CS3, CS6, and CS5 between doses (baseline to post-dose 1 and post-dose 1 to post-dose 2) and from baseline to post-dose 2.

- the percentage of participants achieving an IgG antibody response after the first vaccination (i.e., antibody response is calculated using baseline and Day 7 sample) for LTB and 078 LPS (if sample available);
- the percentage of participants achieving an IgG antibody response after the second vaccination (i.e., antibody response is calculated using baseline and Day 19 sample) for LTB and 078 LPS;
- the percentage of participants achieving an IgG antibody response after either vaccination (i.e., antibody response observed after either vaccination) for LTB and 078 LPS;
- the IgG geometric mean titer (GMT) of LTB and 078 LPS at screening and after each vaccination;
- the IgG geometric mean fold rise(GMFR) of LTB and 078 LPS between doses (baseline to post-dose 1 and post-dose 1 to post-dose 2) and from baseline to post-dose 2.

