12 SUMMARY OF CHANGES IN THE CONDUCT OF THE STUDY OR PLANNED ANALYSES

The primary and secondary immunogenicity endpoints are defined as a 2-fold increase or more in antibody titers between baseline and post-immunization. In addition, each table will also display the results of a 4-fold increase in antibody titers.

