^aA Fold Rise is calculated from baseline. ^bGMT = Geometric mean titer.

	ETVAX (highest safe dose) + 2.5 µg dmLT (N=XX)				ETV. (highest sat 5 µg di (N=X	fe dose) + mLT	All Participants (N=XX)			
Antigen	≥ 2 Fold ^a n (%)	≥ 4 Fold ^a n (%)	GMT ^b (95% CI)	≥ 2 Fold ^a n (%)	$Fold^a \geq 4 \ Fold^a GMT^b \geq$		≥ 2 Fold ^a n (%)	≥ 4 Fold ^a n (%)	GMT ^b (95% CI)	
LTB	xx (xx.x)	xx (xx.x)	xx.x (xx.x, xx.x)	xx (xx.x)	xx (xx.x)	xx.x (xx.x, xx.x)	xx (xx.x)	xx (xx.x)	xx.x (xx.x, xx.x)	
CFA/I	xx (xx.x)	xx (xx.x)	xx.x (xx.x, xx.x)	xx (xx.x)	xx (xx.x)	xx.x (xx.x, xx.x)	xx (xx.x)	xx (xx.x)	xx.x (xx.x, xx.x)	
078 LPS	xx (xx.x)	xx (xx.x)	xx.x (xx.x, xx.x)	xx (xx.x)	xx (xx.x)	xx.x (xx.x, xx.x)	xx (xx.x)	xx (xx.x)	xx.x (xx.x, xx.x)	

^aA Fold Rise is calculated from baseline. ^bGMT = Geometric mean titer.

TABLE 11.3.7.6:

Descriptive Statistics and Analysis of IgG Responses in Plasma Specimens on day 19 (5 days post-dose 2), by Antigen and Treatment Group - Young Children (12 - 23 Months)

TABLE 11.3.7.7:

Descriptive Statistics and Analysis of IgG Responses in Plasma Specimens after either dose, by Antigen and Treatment Group - Young Children (12 - 23 Months)

TABLE 11.3.7.8:

Descriptive Statistics and Analysis of IgG Responses in Plasma Specimens on day 7 post-dose 1, by Antigen and Treatment Group - Infants (6-11 Months)

		cebo =XX)		ETVAX 1/8 Dose (N=XX)		X 1/4 Dose N=XX)	ETVAX 1/2 Dose (N=XX)		
Antigen	≥ 2 Fold ^a n (%)	GMT ^b (95% CI)	≥ 2 Fold ^a n (%)	GMT ^b (95% CI)	≥ 2 Fold ^a n (%)	GMT ^b (95% CI)	≥ 2 Fold ^a n (%)	GMT ^b (95% CI)	
LTB	xx (xx%)	xx.x (xx.x, xx.x)							
078 LPS	xx (xx%)	xx.x (xx.x, xx.x)							

	(highest s 2.5 μg	VAX afe dose) + g dmLT =XX)	(highes 5 μ	TVAX t safe dose) + g dmLT N=XX)	All Participants (N=XX)		
Antigen	≥ 2 Fold ^a GMT ^b n (%) (95% CI)		≥ 2 Fold ^a n (%)	GMT ^b (95% CI)	≥ 2 Fold ^a n (%)	GMT ^b (95% CI)	
LTB	xx (xx%)		xx (xx%)	xx.x (xx.x, xx.x)	xx (xx%)	xx.x (xx.x, xx.x)	
078 LPS	xx (xx%)	xx.x (xx.x, xx.x)	xx (xx%)	xx.x (xx.x, xx.x)	xx (xx%)	xx.x (xx.x, xx.x)	

^aA 2 Fold Rise is calculated from baseline to post dose 2 (Day 19).

TABLE 11.3.7.9:

Descriptive Statistics and Analysis of IgG Responses in Plasma Specimens on day 19 (5 days post-dose 2), by Antigen and Treatment Group - Infants (6-11 Months)

TABLE 11.3.7.10:

Descriptive Statistics and Analysis of IgG Responses in Plasma Specimens after either dose, by Antigen and Treatment Group - Infants (6-11 Months)

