Note: for the last table, a response is ≥2-fold rise at any visit and GMT is based on the maximum post-vaccination titer per participant

^bGMT = Geometric mean titer. This is calculated at post dose 2 (Day 19).

Screened Screened Failed N=XXXN=XXX Reason 1 (N=xxx) Reason 2 (N=xxx) Randomized N=XXX ETVAX Full Dose ETVAX Full Dose + 10 μg Placebo N=XXXdmLT N=XXXReasons Excluded from the Reasons Excluded from the Reasons Excluded from the Safety Population Safety Population Safety Population (N=XXX)(N=XXX)(N=XXX)Reason 1 (N=XXX) Reason 1 (N=XXX) Reason 1 (N=XXX) Reason 2 (N=XXX) Reason 2 (N=XXX) Reason 2 (N=XXX) Safety Population Safety Population Safety Population N=XXXN=XXXN=XXXReasons Excluded from the Reasons Excluded from the Reasons Excluded from the Full Analysis Population Full Analysis Population Full Analysis Population (N=XXX)(N=XXX)(N=XXX)Reason 1 (N=XXX) Reason 1 (N=XXX) Reason 1 (N=XXX) Reason 2 (N=XXX) Reason 2 (N=XXX) Reason 2 (N=XXX) Full Analysis Population Full Analysis Population Full Analysis Population N=XXXN=XXXN=XXXReasons Excluded from the Reasons Excluded from the Reasons Excluded from the **Primary PP Population** Primary PP Population Primary PP Population (N=XXX)(N=XXX)(N=XXX)Reason 1 (N=XXX) Reason 1 (N=XXX) Reason 1 (N=XXX) Reason 2 (N=XXX) Reason 2 (N=XXX) Reason 2 (N=XXX) Primary PP Population Primary PP Population **Primary PP Population** N=XXXN=XXXN=XXX

FIGURE 14.1.1(a): CONSORT Flow Diagram - Adults

FIGURE 14.1.1(b): CONSORT Flow Diagram - Toddlers (24 - 59 Months)

Programming Note: Use same format as Figure 14.1.1a - except use treatment groups: ETVAX 3.5 mL, ETVAX 7mL, ETVAX 14 mL, ETVAX ## + 2.5 μ g dmLT, ETVAX ## + 5 μ g dmLT, ETVAX ## + 10 μ g dmLT, Placebo

FIGURE 14.1.1(c): CONSORT Flow Diagram - Young Children (12 - 23 Months)

Programming Note: Use same format as Figure 14.1.1a - except use treatment groups: ETVAX 3.5 mL, ETVAX 7mL, ETVAX ## + 2.5 μ g dmLT, ETVAX ## + 5 μ g dmLT, Placebo

FIGURE 14.1.1(d): CONSORT Flow Diagram - Infants (6 - 11 Months)

Programming Note: Use same format as Figure 14.1.1a - except use treatment groups: ETVAX 1.75mL, ETVAX 3.5 mL, ETVAX 7mL, ETVAX ## + 2.5 µg dmLT, ETVAX ## + 5 µg dmLT, Placebo

TABLE 14.1.1(a): Ineligibility Summary of Screen Failures - Adults

Inclusion/ Exclusion Category	Inclusion/Exclusion Criterion	Number of Times Item Marked Ineligible
Any	Any inclusion/exclusion criterion	X
Inclusion	Any inclusion criterion	X

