	Placebo vs ETVAX 1/4 Dose	0.xxxx	0.xxxx	0.xxxx				
	Placebo vs ETVAX # mL + 5 μg dmLT	0.xxxx	0.xxxx	0.xxxx				
	Placebo vs ETVAX # mL + 2.5 μg dmLT	0.xxxx	0.xxxx	0.xxxx				
	Combined Treatment Comparisons							
	Combined ETVAX without dmLT vs Combined ETVAX with dmLT	0.xxxx	0.xxxx	0.xxxx				
	Placebo vs Combined ETVAX without dmLT	0.xxxx	0.xxxx	0.xxxx				
	Placebo vs Combined ETVAX with dmLT	0.xxxx	0.xxxx	0.xxxx				

^{*} Using Holm's-Bonferroni adjustment within each antigen, the p-value is statistically significant.

Programming Note: Continue Table 14.2.7.1(c) for each antigen in the following order: CFA/I, CS3, CS6, CS5, and 078 LPT. For each antigen, the Holm's-Bonferroni correction will be performed. If a p-value is statistically significant after the adjustment, a "*" will be placed next to the p-value.

TABLE 14.2.6.1(d): Comparison of Geometric Fold Rise in IgA Titer by Antibody Lymphocyte Secretion - Infants (6 - 11 Months) Full Analysis Population

		P-value from t-test					
Antigen	Comparison	Baseline to Post Dose 1	Baseline to Post Dose 2	Baseline to Any Timepoint			
	Comparing Different Doses of ETVAX without dmLT						
	ETVAX 1/2 Dose vs ETVAX 1/4 Dose	0.xxxx	0.xxxx	0.xxxx			
	ETVAX 1/2 Dose vs ETVAX 1/8 Dose	0.xxxx	0.xxxx	0.xxxx			
	ETVAX 1/4 Dose vs ETVAX 1/8 Dose	0.xxxx	0.xxxx	0.xxxx			
	Comparing Different Doses of ETVAX with dmLT						
	ETVAX # mL + 5 μg dmLT vs ETVAX # mL + 2.5 μg dmLT	0.xxxx	0.xxxx	0.xxxx			
	Comparing ETVAX 1/2 Dose without dmLT with ETVAX with DMLT						
	ETVAX 1/2 Dose vs ETVAX # mL + 5 μg dmLT	0.xxxx	0.xxxx	0.xxxx			
	ETVAX 1/2 Dose vs ETVAX # mL + 2.5 μg dmLT	0.xxxx	0.xxxx	0.xxxx			
	Comparing ETVAX 1/4 Dose without dmLT with ETVAX with DMLT						
LTB	ETVAX 1/4 Dose vs ETVAX # mL + 5 μg dmLT	0.xxxx	0.xxxx	0.xxxx			
	ETVAX 1/4 Dose vs ETVAX # mL + 2.5 μg dmLT	0.xxxx	0.xxxx	0.xxxx			
	Comparing ETVAX 1/8 Dose without dmLT with ETVAX with DMLT						
	ETVAX 1/8 Dose vs ETVAX # mL + 5 μg dmLT	0.xxxx	0.xxxx	0.xxxx			
	ETVAX 1/8 Dose vs ETVAX # mL + 2.5 μg dmLT	0.xxxx	0.xxxx	0.xxxx			
	Comparing Placebo to ETVAX with and without dmLT						
	Placebo vs ETVAX 1/2 Dose	0.xxxx	0.xxxx	0.xxxx			
	Placebo vs ETVAX 1/4 Dose	0.xxxx	0.xxxx	0.xxxx			
	Placebo vs ETVAX 1/8 Dose	0.xxxx	0.xxxx	0.xxxx			
	Placebo vs ETVAX # mL + 5 μg dmLT	0.xxxx	0.xxxx	0.xxxx			
	Placebo vs ETVAX # mL + 2.5 μg dmLT	0.xxxx	0.xxxx	0.xxxx			
	Combined Treatment Comparisons						

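### Two infant table shells contradict the SAP text: the Day 7 plasma IgG table is footnoted to Day 19, and the dose 1 to dose 2 fold-rise comparison is replaced by an undefined one

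*SAP*

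**What the plan says.** **Plasma IgG, infants.** The title of Table 11.3.7.8 (SAP, Appendix I, section 14.1) reads "Descriptive Statistics and Analysis of IgG Responses in Plasma Specimens on day 7 post-dose 1, by Antigen and Treatment Group - Infants (6-11 Months". Footnote a states that the "2 Fold Rise is calculated from baseline to post dose 2 (Day 19". Footnote b, on the GMT, states: "This is calculated at post dose 2 (Day 19". Section 8.3 sets a different rule for the first dose, the percentage of participants "achieving an IgG antibody response after the first vaccination (i.e., antibody response is calculated using baseline and Day 7 sample". Section 12 adds that "each table will also display the results of a 4-fold increase in antibody titers". The infant IgG shell has only a 2-fold column and a GMT column.

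**Fold-rise comparisons, infants.** Section 8.1.3 defines three fold rises for ALS: post-dose 1 over baseline, post-dose 2 over baseline, and a third, "after the second vaccination compared to first vaccination (post vaccination 2 antibody titer/post vaccination 1 antibody titer". It promises t-test p-values for every time period. Sections 8.2.3 and 8.3.3 do the same for fecal and plasma assays, with a Day 29 over baseline ratio added for fecal. In the infant shell 14.2.6.1(d) the third column is headed "Baseline to Any Timepoint".

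**The concern.** Section 8 and the shells give the programmer conflicting instructions for one age group. In the first case, Day 19 data would be printed under a Day 7 title, and the reader of the report would have no sign of it. In the second, a defined contrast is dropped and replaced by one whose value could be the maximum, the first or the last post-dose rise. That choice would be made at programming, after data exist.

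Infants form the largest part of the trial: section 4.3 plans 200, against 45 adults, 150 toddlers and 100 younger children. Infant fold rise is also the only immunogenicity comparison with a power statement (section 5).

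**Working it through.** There is no planned figure to reproduce. The check sets the places side by side and counts how far the second slip spreads.

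**1. Table 11.3.7.8**

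| Place | Time point |
|---|---|
| Title of 11.3.7.8 | Day 7, after dose 1 |
| Footnote a (2-fold response) | baseline to Day 19 |
| Footnote b (GMT) | Day 19 |
| Section 8.3, IgG response after dose 1 | baseline and Day 7 |
| Toddler and younger-children Day 7 IgG shells (11.3.7.2, 11.3.7.5) | from baseline, no Day 19 restriction |
| Title of 11.3.7.9, infants | Day 19 |

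Followed literally, 11.3.7.8 and 11.3.7.9 hold the same numbers. Footnote b is printed a little after the shell in the extracted text, but its letter matches the GMT column heading. If the footnotes were meant for all three infant IgG tables that share the shell, they would still fit only 11.3.7.9, because 11.3.7.10 has its own note based on any visit and the maximum titer.

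4-fold column: present in the adult (11.3.7.1), toddler (11.3.7.2) and younger-children (11.3.7.5) IgG shells, absent in the infant shell.

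**2. Table 14.2.6.1(d)**

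| Place | Third fold-rise contrast |
|---|---|
| Sections 8.1.3, 8.2.3, 8.3.3 | post-dose 2 over post-dose 1 |
| Comparison shells 14.2.6.1(a), (b), (c) | post-dose 1 to post-dose 2 |
| Infant descriptive table 14.2.5.1(d) | post-dose 1 to post-dose 2 |
| Infant comparison shell 14.2.6.1(d) | baseline to any timepoint |

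So the infant comparison table does not match its own descriptive table. The same stray heading sits in the infant Fisher's-test shell 14.2.1.3(d), where it is proper because section 8.1.1 defines a response at any time point. That points to copying. The nearest definitions elsewhere (footnote c of 11.3.7.1 and the note to 11.3.7.10) concern response and GMT, not a fold rise.

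**3. Spread**

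- Source shell: 14.2.6.1(d).
- ALS, per protocol: 14.2.6.2(d). Its note cites 14.2.7.1(d), which is the number section 8.1.3 gives to this fold-rise comparison, so it is read here as pointing to the same shell.
- Fecal: 14.2.12.1(d) and 14.2.12.2(d). The note adds Day 28 but does not restore the lost column.
- Plasma IgA: 14.2.18.1(d) and 14.2.18.2(d).
- Plasma IgG: 14.2.24.1(d) and 14.2.24.2(d).

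Total: 1 + 1 + 2 + 2 + 2 = 8 infant tables.

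Comparisons listed in the shell: 3 + 1 + 2 + 2 + 2 + 5 + 3 = 18. Assay-antigen pairs: 6 ALS + 6 fecal + 6 plasma IgA + 2 plasma IgG = 20. At most 18 × 20 = 360 dose 1 to dose 2 p-values are lost per analysis population, and 2 × 360 = 720 over both. These are upper bounds: O78 LPS in ALS and fecal depends on sample, the programming guidelines allow that not every antigen is analysed, and section 8 runs both populations only if they differ.

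**The case against.** The case for treating this as editorial is fair in several respects.

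- Section 8 is unambiguous and the preface calls the shells samples, so a careful programmer would follow the text. But the shells and their notes are what fix columns and footnotes, and nothing in the SAP says the text prevails.
- Sections 8.1.4, 8.2.4 and 8.3.4 use Day 19 for in-text tables, so the Day 19 footnotes may be a leftover from a single-time-point layout. That explains the slip without curing it: section 8.3.4 covers IgA, and the in-text tables now include separate Day 7 tables.
- The comparisons are declared exploratory (sections 6.8 and 8). That limits the harm; it does not define the column.

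Four stronger readings are tempting, and the SAP does not support them.

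- *Infants have no assessment of whether dose 2 adds to dose 1.* That is a within-group question. It is answered by the post-dose 1 to post-dose 2 GMFR and its 95% CI, which stay in 14.2.5.1(d) and in its reuses for fecal (14.2.11), plasma IgA (14.2.17) and plasma IgG (14.2.23). Only the comparison of that increment between arms is lost.
- *Infant Day 7 or 4-fold IgG results vanish from the report.* They remain in 14.2.19.1(d) and (h), 14.2.20.1(d) and 14.2.23.1(d). The loss is confined to the in-text tables.
- *The replacement column would show an inflated rise.* A maximum over visits does inflate each arm, but this shell prints only between-group p-values. With equal sampling and variance across arms the inflation largely cancels.
- *The Holm adjustment is distorted.* Swapping one column for another leaves the number of tests unchanged.

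**Conclusion.** Both contradictions stand on the face of the SAP and should be corrected. The consequences are limited: one in-text infant table that would carry Day 19 results under a Day 7 title and without the 4-fold column, and eight infant comparison tables in which a defined between-group t-test gives way to an undefined one. No other age group is affected. The baseline contrasts, including the post-vaccination over baseline fold rise on which the section 5 power statement rests, are untouched.

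This rests on two readings. Footnote b is taken to belong to Table 11.3.7.8, and the note to 14.2.6.2(d) is taken to point to the ALS fold-rise shell despite its outdated number. Without the first, footnote a alone still contradicts the title. Without the second, seven tables are affected, not eight.

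**What to change.** - In Table 11.3.7.8, define the response as baseline to Day 7 and the GMT at Day 7. Keep the Day 19 footnotes for Table 11.3.7.9 only, and leave 11.3.7.10 with its own note.
- Add the 4-fold column to the infant IgG shell, which 11.3.7.9 and 11.3.7.10 also use.
- In Table 14.2.6.1(d), replace the third column heading with post-dose 1 to post-dose 2, and confirm that the seven tables that reuse it follow. Update the table number in the note to 14.2.6.2(d) at the same time.
- If a fold rise from baseline to any time point is wanted, define it in sections 8.1.3, 8.2.3 and 8.3.3 and add it for every age group, alongside the dose 1 to dose 2 contrast.

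The cost is shell edits only, with no new data, visits or assays.

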08 AUG 2018

Version 2.0

TABLE 14.1.4.1(c):
Summary of Categorical Demographic and Baseline Characteristics by Treatment Group - Young Children (12 - 23 Months)

		Placebo (N=XX)		ETVAX 1/4 Dose (N=XX)		ETVAX 1/2 Dose (N=XX)		Combined ETVAX Alone (N=XX)	
Demographic Category	Characteristic	n	%	n	%	n	%	n	%
C	Male	XX	xx.x	XX	xx.x	XX	XX.X	XX	XX.X
Sex	Female	XX	xx.x	XX	xx.x	XX	XX.X	XX	XX.X
	Black	XX	xx.x	XX	xx.x	XX	XX.X	XX	XX.X
Race	White	XX	xx.x	XX	xx.x	XX	XX.X	XX	XX.X
Race	Asian	XX	xx.x	XX	xx.x	XX	XX.X	XX	XX.X
	Unknown	XX	xx.x	XX	xx.x	XX	XX.X	XX	XX.X
	None	xx	xx.x	xx	XX.X	XX	XX.X	XX	XX.X
Weight for age	Mild	XX	XX.X	XX	xx.x	XX	XX.X	XX	XX.X
malnutrition (underweight)	Moderate	XX	xx.x	XX	xx.x	XX	XX.X	XX	XX.X
(underweight)	Severe	XX	xx.x	XX	xx.x	XX	XX.X	XX	XX.X
	None	xx	xx.x	XX	xx.x	XX	XX.X	XX	XX.X
Heigtht for age malnutrition	Mild	XX	xx.x	XX	xx.x	XX	XX.X	XX	XX.X
(stunting)	Moderate	XX	XX.X	XX	xx.x	XX	XX.X	XX	XX.X
(stuning)	Severe	XX	XX.X	XX	xx.x	XX	XX.X	XX	XX.X
	None	xx	xx.x	XX	xx.x	XX	XX.X	XX	XX.X
Weight for Height malnutrtion	Mild	XX	xx.x	XX	xx.x	XX	XX.X	XX	XX.X
(wasting)	Moderate	XX	xx.x	XX	xx.x	XX	XX.X	XX	XX.X
	Severe	XX	xx.x	XX	xx.x	XX	XX.X	XX	XX.X

TABLE 14.1.4.1(c): Continued
Summary of Categorical Demographic and Baseline Characteristics by Treatment Group - Young Children (12 - 23 Months)

		ETVAX (highest safe dose) + 2.5 µg dmLT (N=XX)		ETVAX (highest safe dose) + 5 µg dmLT (N=XX)		Combined ETVAX + dmLT (N=XX)		All Participants (N=XX)	
Demographic Category	Characteristic	n	%	n	%	n	%	n	%
Sex	Male	XX	XX.X	XX	xx.x	XX	XX.X	XX	XX.X
SCX	Female	xx	xx.x	xx	xx.x	xx	XX.X	XX	XX.X
	Black	xx	XX.X	xx	xx.x	XX	XX.X	XX	XX.X
Race	White	xx	XX.X	XX	XX.X	XX	XX.X	XX	XX.X
Race	Asian	XX	XX.X	XX	xx.x	XX	XX.X	XX	XX.X
	Unknown	XX	XX.X	XX	xx.x	XX	XX.X	XX	XX.X
	None	xx	XX.X	XX	xx.x	XX	XX.X	XX	XX.X
Weight for age	Mild	XX	XX.X	XX	xx.x	XX	XX.X	XX	XX.X
malnutrition (underweight)	Moderate	XX	XX.X	XX	xx.x	XX	XX.X	XX	XX.X
(under weight)	Severe	xx	XX.X	XX	xx.x	XX	XX.X	XX	XX.X
Heigtht for age	None	xx	XX.X	XX	xx.x	XX	XX.X	XX	XX.X
malnutrition	Mild	XX	XX.X	XX	xx.x	XX	XX.X	XX	XX.X
(stunting)	Moderate	XX	XX.X	XX	xx.x	XX	XX.X	XX	XX.X
	Severe	xx	XX.X	XX	xx.x	XX	XX.X	XX	XX.X
Weight for Height	None	xx	XX.X	XX	xx.x	XX	XX.X	XX	XX.X
malnutrtion	Mild	XX	XX.X	XX	xx.x	XX	XX.X	XX	XX.X
(wasting)	Moderate	xx	XX.X	XX	xx.x	XX	XX.X	XX	XX.X
	Severe	XX	XX.X	XX	XX.X	XX	XX.X	XX	XX.X

N = Number of participants in the Safety population. n = Number of participants reporting the response.

TABLE 14.1.4.1(d): Summary of Categorical Demographic and Baseline Characteristics by Treatment Group - Infants (6 - 11 Months)

		Placebo (N=XX)			ETVAX 1/8 Dose (N=XX)		ETVAX 1/4 Dose (N=XX)		ETVAX 1/2 Dose (N=XX)		d ETVAX one XX)
Demographic Category	Characteristic	n	0/0	n	%	n	%	n	%	n	%
	Male	XX	XX.X	XX	XX.X	XX	XX.X	XX	XX.X	XX	XX.X
Sex	Female	XX	XX.X	XX	XX.X	XX	XX.X	XX	XX.X	XX	XX.X
	Black	XX	XX.X	XX	XX.X	XX	XX.X	XX	XX.X	XX	XX.X
Race	White	XX	XX.X	XX	XX.X	XX	XX.X	XX	XX.X	XX	XX.X
Race	Asian	XX	XX.X	XX	XX.X	XX	XX.X	XX	XX.X	XX	XX.X
	Unknown	XX	XX.X	XX	XX.X	XX	XX.X	XX	XX.X	XX	XX.X
	None	XX	XX.X	XX	XX.X	XX	XX.X	XX	XX.X	XX	XX.X
Weight for age	Mild	XX	XX.X	XX	XX.X	XX	XX.X	XX	XX.X	XX	XX.X
malnutrition	Moderate	XX	XX.X	XX	XX.X	XX	XX.X	XX	XX.X	XX	XX.X
(underweight)	Severe	XX	XX.X	XX	XX.X	XX	XX.X	XX	XX.X	XX	XX.X
Heigtht for age	None	XX	XX.X	XX	XX.X	XX	XX.X	XX	XX.X	XX	XX.X
malnutrition	Mild	XX	XX.X	XX	XX.X	XX	XX.X	XX	XX.X	XX	XX.X
(stunting)	Moderate	XX	XX.X	XX	XX.X	XX	XX.X	XX	XX.X	XX	XX.X
	Severe	XX	XX.X	XX	XX.X	XX	XX.X	XX	XX.X	XX	XX.X
Weight for height	None	XX	XX.X	XX	XX.X	XX	XX.X	XX	XX.X	XX	XX.X
malnutrtion	Mild	XX	XX.X	XX	XX.X	XX	XX.X	XX	XX.X	XX	XX.X
(wasting)	Moderate	XX	XX.X	XX	XX.X	XX	XX.X	XX	XX.X	XX	XX.X
	Severe	XX	XX.X	XX	XX.X	XX	XX.X	XX	XX.X	XX	XX.X

N = Number of participants in the Safety population. n = Number of participants reporting the response.

TABLE 14.1.4.1(d): Continued Summary of Categorical Demographic and Baseline Characteristics by Treatment Group - Infants (6 - 11 Months)

	aphic		ETVAX (highest safe dose) + 2.5 µg dmLT (N=XX)		ETVAX (highest safe dose) + 5 µg dmLT (N=XX)		oined + dmLT XX)	All Participants (N=XX)	
Demographic Category	Characteristic	n	%	n	%	n	%	n	%
Sex	Male	XX	XX.X	XX	XX.X	XX	XX.X	XX	XX.X
Sex	Female	XX	XX.X	XX	xx.x	XX	XX.X	XX	XX.X
	Black	XX	XX.X	xx	XX.X	XX	XX.X	XX	XX.X
Race	White	XX	XX.X	XX	xx.x	XX	XX.X	XX	XX.X
Race	Asian	XX	XX.X	XX	xx.x	XX	XX.X	XX	XX.X
	Unknown	XX	xx.x	xx	xx.x	XX	XX.X	XX	XX.X
	None	XX	xx.x	XX	xx.x	xx	XX.X	XX	XX.X
Weight for age	Mild	XX	XX.X	XX	xx.x	XX	XX.X	XX	XX.X
malnutrition (underweight)	Moderate	XX	XX.X	XX	xx.x	XX	XX.X	XX	XX.X
(underweight)	Severe	XX	xx.x	XX	xx.x	xx	XX.X	XX	XX.X
Heigtht for age	None	XX	XX.X	xx	XX.X	XX	XX.X	XX	XX.X
malnutrition	Mild	XX	XX.X	XX	xx.x	XX	XX.X	XX	XX.X
(stunting)	Moderate	XX	XX.X	XX	xx.x	XX	XX.X	XX	XX.X
	Severe	XX	XX.X	xx	xx.x	XX	XX.X	XX	XX.X
Weight for Height	None	XX	XX.X	xx	xx.x	XX	XX.X	XX	XX.X
malnutrtion	Mild	XX	XX.X	XX	XX.X	XX	XX.X	XX	XX.X
(wasting)	Moderate	XX	XX.X	xx	xx.x	XX	XX.X	XX	XX.X
	Severe	XX	xx.x	XX	xx.x	XX	XX.X	XX	XX.X

N = Number of participants in the Safety population. n = Number of participants reporting the response.

TABLE 14.1.4.2(a): Summary of Continuous Demographic and Baseline Characteristics by Treatment Group - Adults

Variable	Statistic	Placebo (N=XX)	ETVAX Full Dose (N=XX)	ETVAX Full Dose + 10 µg dmLT (N=XX)	All Participants (N=XX)
	n	X	X	X	X
	Mean	X.X	X.X	X.X	X.X
	Standard Deviation	X.XX	X.XX	X.XX	X.XX
A 00 (1100mg)	Median	X	X	X	X
Age (years)	25th Percentile	X.X	X.X	X.X	X.X
	75th Percentile	X.X	X.X	X.X	X.X
	Minimum	X	X	X	X
	Maximum	X	X	X	X
	n	X	X	X	X
	Mean	XX.XX	X.XX	X.XX	X.XX
	Standard Deviation	x.xxx	X.XXX	X.XXX	X.XXX
Haight (am)	Median	X.X	X.X	X.X	X.X
Height (cm)	25th Percentile	X.XX	X.XX	X.XX	X.XX
	75th Percentile	x.xx	X.XX	X.XX	X.XX
	Minimum	X.X	X.X	X.X	X.X
	Maximum	X.X	X.X	X.X	X.X
	n	X	X	X	X
	Mean	XX.XX	X.XX	X.XX	X.XX
	Standard Deviation	x.xxx	X.XXX	x.xxx	X.XXX
Waight (Ira)	Median	X.X	X.X	X.X	X.X
Weight (kg)	25th Percentile	x.xx	X.XX	X.XX	X.XX
	75th Percentile	X.XX	X.XX	X.XX	X.XX
	Minimum	X.X	X.X	X.X	X.X
	Maximum	X.X	X.X	X.X	X.X

N = Number of participants in the Safety population. n = Number of participants with a response.

TABLE 14.1.4.2(b): Summary of Continuous Demographic and Baseline Characteristics by Treatment Group - Toddlers (24 - 59 Months)

Variable	Statistic	Placebo (N=XX)	ETVAX 1/4 Dose (N=XX)	ETVAX 1/2 Dose (N=XX)	ETVAX Full Dose (N=XX)	Combined ETVAX Alone (N=XX)
	n	X	X	X	X	X
	Mean	X.X	X.X	X.X	X.X	X.X
	Standard Deviation	X.XX	X.XX	X.XX	X.XX	X.XX
Aga (months)	Median	X	X	X	X	X
Age (months)	25th Percentile	X.X	X.X	X.X	X.X	X.X
	75th Percentile	X.X	X.X	X.X	X.X	X.X
	Minimum	X	X	X	X	X
	Maximum	X	X	X	X	X
	n	Х	X	X	Х	X
	Mean	XX.XX	X.XX	X.XX	X.XX	X.XX
	Standard Deviation	x.xxx	x.xxx	X.XXX	x.xxx	X.XXX
r (1 ()	Median	X.X	X.X	X.X	X.X	X.X
Length (cm)	25th Percentile	X.XX	X.XX	X.XX	X.XX	X.XX
	75th Percentile	X.XX	X.XX	X.XX	X.XX	X.XX
	Minimum	X.X	X.X	X.X	X.X	X.X
	Maximum	X.X	X.X	X.X	X.X	X.X
	n	Х	X	X	Х	X
	Mean	XX.XX	X.XX	X.XX	X.XX	X.XX
	Standard Deviation	x.xxx	x.xxx	X.XXX	x.xxx	X.XXX
W : 1. (1.)	Median	X.X	X.X	X.X	X.X	X.X
Weight (kg)	25th Percentile	X.XX	X.XX	X.XX	X.XX	X.XX
	75th Percentile	x.xx	X.XX	X.XX	X.XX	X.XX
	Minimum	X.X	X.X	X.X	X.X	X.X
	Maximum	X.X	X.X	X.X	X.X	X.X

N = Number of participants in the Safety population. n = Number of participants with a response.

TABLE 14.1.4.2(b): Continued
Summary of Continuous Demographic and Baseline Characteristics by Treatment Group - Toddlers (24 - 59 Months)

Variable	Statistic	ETVAX (highest safe dose) + 2.5 µg dmLT (N=XX)	ETVAX (highest safe dose) + 5 µg dmLT (N=XX)	ETVAX (highest safe dose) + 10 µg dmLT (N=XX)	Combined ETVAX + dmLT (N=XX)	All Participants (N=XX)
	n	X	X	X	X	X
	Mean	X.X	X.X	X.X	X.X	X.X
	Standard Deviation	X.XX	X.XX	X.XX	X.XX	X.XX
A (41)	Median	Х	X	X	Х	X
Age (months)	25th Percentile	X.X	X.X	X.X	X.X	X.X
	75th Percentile	X.X	X.X	X.X	X.X	X.X
	Minimum	Х	X	X	Х	X
	Maximum	Х	X	X	Х	X
	n	Х	X	X	Х	X
	Mean	XX.XX	X.XX	X.XX	X.XX	X.XX
	Standard Deviation	X.XXX	x.xxx	x.xxx	X.XXX	X.XXX
I (1 ()	Median	X.X	X.X	X.X	X.X	X.X
Length (cm)	25th Percentile	X.XX	X.XX	X.XX	X.XX	X.XX
	75th Percentile	X.XX	X.XX	X.XX	X.XX	X.XX
	Minimum	X.X	X.X	X.X	X.X	X.X
	Maximum	X.X	X.X	X.X	X.X	X.X
	n	Х	X	X	X	X
	Mean	XX.XX	X.XX	X.XX	X.XX	X.XX
	Standard Deviation	X.XXX	x.xxx	x.xxx	X.XXX	X.XXX
W-:-1.4 (1)	Median	X.X	X.X	X.X	X.X	X.X
Weight (kg)	25th Percentile	X.XX	X.XX	X.XX	X.XX	x.xx
	75th Percentile	X.XX	X.XX	X.XX	X.XX	X.XX
	Minimum	X.X	X.X	X.X	X.X	X.X
	Maximum	X.X	X.X	X.X	X.X	X.X

N = Number of participants in the Safety population. n = Number of participants with a response.

